4.5.5.2 Collection of Unsolicited Adverse Events and COVID-19 Exposure/Symptoms

Weekly and monthly phone calls and clinic visits (Section 4.5.3) including unscheduled and ET, if applicable) will be used to collect unsolicited AEs and COVID-19 exposure/symptoms:

- Unsolicited AEs will be recorded through Final Visit or ET Visit. For unsolicited AEs categorized as AEs leading to discontinuation/withdrawal, medically attended adverse events (MAAEs), and serious adverse events (SAEs) documentation will occur through 365 days after the completion of the initial vaccination series (up to Day 394).
- Symptoms of COVID-19 (Section 4.5.3.7 and Appendix 2) or exposure to SARS-CoV-2 will be recorded from first study vaccine administration throughout the entire study (Final Visit or ET Visit).
- Any participant reporting onset of a possible symptom of COVID-19 or a possible exposure to SARS-CoV-2 should trigger an Unscheduled Visit (Section 4.5.3.7) for further evaluation. This visit should ideally occur within 72 hours of COVID-19 symptom onset or reported SARS-CoV-2 exposure. Should the participant manifest symptoms within the first 4 days after each vaccination, refer to Section 4.5.3.7 for further consideration.

4.5.5.3 Blood and SARS-CoV-2 Sampling

Blood and SARS-CoV-2 sampling will be collected as follows:

- At Screening:

In all participants:

- Blood may be drawn for pregnancy testing at sites that do not allow urine pregnancy testing.
- Blood may be drawn for FSH measurement in a female to confirm menopausal status (Appendix 3).

- Nasal swab testing for SARS-CoV-2 by RT-PCR. An additional sample will be collected and retained in the event of SARS-CoV-2 sequencing for possible variant determination. If obtained within 5 days prior to Screening period, nasal swab testing does not need to be repeated at Screening.

In Phase 1 participants:

- Blood will be drawn for additional screening assessments (complete blood count [CBC], chemistry panel, and virology [HbsAg, HCV Ab, HIV]). At Screening, in addition to sending samples to the central laboratory, a locally processed sample can be used for eligibility for enrollment. Samples will be obtained prior to study vaccine administration.

- Day 1:

In all participants:

- Antibody assessments for SARS-CoV-2 seropositivity for nucleocapsid antigen will be performed.
- Blood will be drawn and saved as a baseline sample for a possible future analysis of the correlate of protection and possible future analysis for immune responses to SARS-CoV-2 variants.
- Nasal swab testing for SARS-CoV-2 by RT-PCR. If Screening test is within 5 days of Day 1, nasal swab testing does not need to be repeated at Day 1. If screening and randomization are being performed on the same day the result of the RT-PCR test must be known to be negative prior to randomization.

In Phase 1/2/3a and Phase 3c-1 participants:

- Blood will be drawn as a baseline sample for testing of SARS-CoV-2 antibody responses.

- Day 8

In Phase 1 participants:

- Blood will be drawn for safety laboratory assessments (CBC and chemistry panel).

- Day 29

In Phase 1 participants:

- Blood will be drawn for safety laboratory assessments (CBC and chemistry panel), prior to study vaccine administration.

In all participants:

- Antibody assessments for SARS-CoV-2 seropositivity for nucleocapsid antigen will be performed.

In Phase 1/2/3a and Phase 3c-1 participants:

- Blood will be drawn for testing of SARS-CoV-2 antibody responses. An archive sample will also be drawn for potential future analysis for immune responses to SARS-CoV-2 variants.
- Day 36
 - In Phase 1 participants:
 - Blood will be drawn for safety laboratory assessments (CBC and chemistry panel).
- Day 57:
 - In Phase 1 participants:
 - Blood will be drawn for safety laboratory assessments (CBC and chemistry panel).
- In all participants:
 - Blood will be drawn and saved for a possible future analysis of a correlate of protection and possible future analysis for immune responses to SARS-CoV-2 variants.
- In Phase 1/2/3a and the Phase 3c-1 participants:
 - Blood will be drawn for testing of SARS-CoV-2 antibody responses, including anti-nucleocapsid antibody responses.
- Day 92 (Cohorts 1/2/3a and 3b only):
 - In Phase 1/2/3a participants:
 - Blood will be drawn for testing of SARS-CoV-2 antibody responses, including anti-nucleocapsid antibody responses. An archive sample will also be drawn for potential future analysis for immune responses to SARS-CoV-2 variants.
- Day 120 (Cohorts 1/2/3a and 3b only):
 - In Phase 2/3a participants:
 - Blood will be drawn for testing of SARS-CoV-2 antibody responses, including anti-nucleocapsid antibody responses. An archive sample will also be drawn for potential future analysis for immune responses to SARS-CoV-2 variants.
- Day 211 (Cohort 3c-1 only)
 - Blood will be drawn for testing of SARS-CoV-2 antibody responses, including anti-nucleocapsid antibody responses. An archive sample will also be drawn for potential future analysis for immune responses to SARS-CoV-2 variants.

- Unscheduled Visits:

In all participants that have COVID-19 symptoms and/or COVID-19 exposure, the participant is asked to contact the site as soon as feasible to make arrangements for testing.

The preferred assessment is to evaluate for SARS-CoV-2 via nasal swab. Testing of the nasal swab will be performed as follows:

- To measure SARS-CoV-2 by reverse transcriptase-polymerase chain reaction (RT-PCR).
- An additional sample will be collected and retained in the event of SARS-CoV-2 sequencing for possible variant determination.
- In some cases, such as when the participant lives remote from the study site, the participant may be given two test kits to take home as it may be necessary to perform a rapid antigen test prior to bringing the participant to the site for nasal swab RT-PCR testing. In such instances, if the first rapid antigen test is negative then a SECOND test should be performed 48 to 72 hours later.
- Note: For Phase 1/2/3a/3b, nasal swabs for RT-PCR test do not need to be performed after Day 92. For Phase 3c, nasal swabs should continue to be collected until the last study visit (early termination of Day 394).

- Day 394 (Final Visit); or ET:

In the Immunogenicity Subgroup Participants:

Blood will be drawn for testing of SARS-CoV-2 antibody responses, including anti-nucleocapsid antibody responses. An archive sample will also be drawn for potential future analysis for immune responses to SARS-CoV-2 variants.

4.5.5.4 Telephone Calls

Telephone calls will be performed at intervals specified in Section [4.5.3](#) and the schedule of assessments ([Appendix 1](#)) for the following reasons:

- To determine if any solicited AEs are persisting longer than 7 days after each study vaccination
- To evaluate for unsolicited AEs (including MAAEs, SAEs, AEs leading to discontinuation/withdrawal)
- To collect information for concomitant medication/vaccines
- To evaluate for symptoms of COVID-19 disease and risks of exposure to COVID-19. Solicitation of symptoms and risks of exposure to COVID-19 will follow a scripted interview provided in the Investigator Site File

Calls to the participant will be performed by a trained site team member designated by the investigator. However, in the event the participant reports any change in health status or change in medications, a qualified health care practitioner will need to complete the safety assessment.

4.5.5.5 Physical Examinations

For participants in Phase 1, complete physical examination will be performed at Screening, Days 1, 8, 29, 36, 92 and 120, and Final Visit (or ET). For Phase 2, 3a and 3b complete physical examination will be performed at Screening, Days 1 and 29, 92 and 120, and Final Visit (or ET). For participants in Phase 3c complete physical examination will be performed at Screening, Days 1 and 29, and Final Visit (or ET). Symptom-directed examination (if any symptoms) may be performed at other timepoints as indicated to assess changes from Screening.

- A complete physical examination will include, at a minimum, assessments of the general status of the participant, the skin of the intended study vaccine administration site, superficial lymph nodes, cardiovascular, respiratory, gastrointestinal, and neurological systems.
- A directed physical examination will include, at a minimum, assessments of the skin of the intended/actual study vaccine administration site, and/or any organ systems relevant to symptoms or AEs reported by the participant. Investigators should pay special attention to clinical signs related to previous serious illnesses.

Physical examination is to be performed by a qualified health care practitioner designated by the investigator.

4.5.5.6 Height and Weight

At Screening, height and weight will be measured and recorded using calibrated instruments. Body mass index for “at risk” determination will be calculated using these values.

4.5.5.7 Vital Signs, Body Temperature, and Pulse Oximetry

Vital signs will be obtained at each clinic visit. Vital signs will be measured in a semi-supine position after 5 minutes of rest and will include systolic and diastolic blood pressure, heart rate, and respiratory rate.

Body temperature will be measured according to standard of care and thermometer instructions. If body temperature is taken orally, the participant should not have consumed hot or cold beverages or smoked within 15 minutes prior to measurement.

Pulse oximetry will be performed at Unscheduled Visits, if warranted, to evaluate symptoms of COVID-19. Vital sign measurements are to be performed by a qualified health care practitioner designated by the investigator.

4.5.5.8 Pregnancy Testing

For women of childbearing potential (refer to [Appendix 3](#) for definition), urine pregnancy testing (“dipstick” test) will be performed at the sites, if available and permissible by local policy, prior to each vaccination dose. The site may perform serum testing of beta human chorionic gonadotropin if this is required by policy. The test may be performed at the local laboratory or central laboratory. The results of the pregnancy test must be read before each dose of study vaccine, and the result must be recorded in the source documents.

4.5.5.9 Medical History

At Screening, medical history will also be collected including, but not limited to, any medical history that may be relevant to participant eligibility for study participation such as prior vaccinations, concomitant medications/vaccines, and previous and ongoing illnesses or injuries. Relevant medical history can also include any medical history that contributes to the understanding of an AE that occurs during study participation if it represents an exacerbation of an underlying disease/pre-existing problem. Medical history and vaccination history should be obtained for a minimum of, but not limited to, the 2-month period prior to enrollment.

Vaccination history specifically for COVID-19, SARS-CoV, or Middle East respiratory syndrome (MERS) must include **any** known exposure to these investigational or authorized vaccines.

Should review of on-study AEs or concomitant medications determine that there was a pre-existing medical condition present but not captured at Screening, this medical condition should be added to the Medical History.

5 PARTICIPANT SELECTION AND WITHDRAWAL CRITERIA

5.1 Selection of Study Participants

Study sites may be selected based on SARS-CoV-2 infection risk of the local population.

Participants will be assigned to study treatment only if they meet all the inclusion criteria and none of the exclusion criteria.

Participants who withdraw from the study after randomization will not be replaced.

Deviations from the inclusion and exclusion criteria are not allowed because they can potentially jeopardize the scientific integrity of the study, regulatory acceptability, or participant safety. Therefore, adherence to the eligibility criteria as specified in the protocol is essential.

5.1.1 Inclusion Criteria

Each participant must meet all the following criteria to be enrolled in this study:

Consent and Compliance

1. Individuals or legally authorized representatives must freely provide consent to study participation.
2. Individuals must agree to comply with all study visits and procedures (including blood and nasal swab sampling, Diary completion, receipt of telephone calls from the site, willingness to be available for Unscheduled clinic visits).
3. Individuals in Phase 1 and Phase 2 must have access to and be capable of using an eDiary.
4. Individuals of childbearing potential who are sexually active must be willing to adhere to contraceptive requirements ([Appendix 3](#)).

Type of Participant

5. Adult males or females of at least 18 years of age at the time of signing of the informed consent.
6. Individuals considered at risk for COVID-19 due to work or living environment in the opinion of the Investigator.

5.1.2 Exclusion Criteria

Individuals meeting any of the following criteria will be excluded from the study:

Medical Conditions

1. Significant infection or other acute illness, including body temperature $>100.4^{\circ}\text{F}$ ($>38.0^{\circ}\text{C}$) on the day prior to or Day 1. Participants meeting this criterion may be rescheduled within the relevant window periods (Section [5.2.1](#)). Afebrile participants with minor illnesses can be enrolled at the discretion of the investigator.
2. Pregnant or breastfeeding.

3. Known history of COVID-19 (nucleocapsid positive test is not exclusionary) or positive nasal swab SARS-CoV-2 by RT-PCR test. Note: if obtained within 5 days prior to Screening period, do not need to repeat RT-PCR at Screening.
4. Close contact with a person known to be SARS-CoV-2 positive or with a clinical diagnosis of COVID-19 within 7 days prior to enrollment. Participants meeting this criterion who remain asymptomatic for 7 days may be rescheduled for enrollment within the relevant window periods (Section 5.2.1).
5. Known history of anaphylaxis, urticaria, or other significant adverse reaction to the vaccine or its excipients. See the Investigator's Brochure for list of vaccine components.
6. Known history of anaphylaxis to other vaccines.
7. Bleeding disorder considered a contraindication to intramuscular (IM) injection or phlebotomy.
8. Immunosuppressive or immunodeficient state, asplenia, recurrent severe infections, or known to be HIV positive.
9. An underlying clinically significant acute or chronic medical condition or physical examination findings for which, in the opinion of the investigator, participation would not be in the best interest of the participant (eg, compromise the well-being) or that could prevent, limit, or confound the protocol-specified assessments.

Prior/Concomitant Therapy

10. Has previously received investigational or approved MERS-CoV, SARS-CoV, SARS-CoV-2 vaccines or who have plans to receive off-study COVID-19 vaccines.
11. Has received a live replicating vaccine within 28 days prior to each study vaccination or a licensed inactivated or non-replicating vaccine within 14 days prior to first study vaccination.
12. Has received treatment with immunosuppressive therapy, including cytotoxic agents or systemic corticosteroids, eg, for cancer or an autoimmune disease, within 6 months prior to Screening, or planned receipt throughout the study. If systemic corticosteroids have been administered short term (<14 days) for treatment of an acute illness, participants should not be enrolled into the study until corticosteroid therapy has been discontinued for at least 28 days prior to first study vaccine administration. Inhaled/nebulized, intra-articular, intrabursal, or topical (skin or eyes) corticosteroids are permitted.
13. Has received systemic immunoglobulins or blood products within 3 months prior to first study vaccine administration or plans to receive such products during the study.

Other Exclusions

14. Demonstrated inability to comply with the study procedures.
15. Investigator site staff members, employees of the Sponsor or the CRO directly involved in the conduct of the study, or site staff members otherwise supervised by the investigator, or immediate family members of any of the previously mentioned individuals.

Additional Exclusion Criteria for Phase 1 Participants Only

16. Individuals \geq 60 years of age.
17. Individuals with clinically significant abnormalities in medical history or physical examination, including but not limited to, the following:
 - a) Respiratory disease (e.g., chronic obstructive pulmonary disease [COPD], asthma) requiring daily medications or oxygen currently or any treatment of respiratory disease exacerbations (e.g., COPD or asthma exacerbation) warranting hospitalization or an emergency room visit or supplemental oxygen in the last 5 years.
 - b) Significant cardiovascular disease (e.g., congestive heart failure, cardiomyopathy, ischemic heart disease) or history of myocarditis or pericarditis as an adult.
 - c) Neurological or neurodevelopmental conditions (e.g., migraines, epilepsy, stroke, seizures in the last 3 years, encephalopathy, focal neurologic deficits, Guillain-Barré syndrome, encephalomyelitis or transverse myelitis).
 - d) Significant hematologic abnormalities (e.g., sickle cell disease, beta thalassemia, coagulation disorders).
 - e) Major surgery within the past 6 months.
 - f) Individuals with a history of chronic liver disease.
18. Individuals with the following abnormal Screening laboratory results:
 - a) Positive nasal swab SARS-CoV-2 by RT-PCR test. Note: if obtained within 5 days prior to Screening period, do not need to repeat RT-PCR at Screening.
 - b) Alanine aminotransferase (ALT), aspartate aminotransferase (AST), gamma-glutamyl transferase (GGT), total bilirubin, or alkaline phosphatase >1.5 upper limit of normal.
 - c) Hemoglobin <9.5 g/dL for females and <10.5 g/dL for males.
 - d) Platelet count $<100 \times 10^9$ /L.
 - e) Other clinically significant abnormal (according to the judgment of the Investigator) Screening laboratory values.
 - f) Individuals with Type 2 diabetes and Screening hemoglobin A1c $>8.0\%$.
 - g) Hepatitis B core antigen (HbsAg), Hepatitis C virus (HCV) antibody or HIV positive.

Additional Exclusion Criteria for Phase 3c Participants Only

19. No contraindications (as specified in the prescribing information) to receiving the ChAdOx1 vaccine.

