5.1.4 Screen Failures

Screen failures are individuals who fail to meet all inclusion criteria or who meet at least 1 of the exclusion criteria. Rescreening will not be permitted but enrollment may be delayed if the entry criterion is specific to a time window; see Section [5.2.1](#). Reasons for screen failure will be collected and entered in the electronic data capture (EDC) system.

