The primary purpose of this amendment is to add to the design that participants in Phase 2 and 3a who received ARCT-154 in the initial vaccination series will be further randomized to receive a 3rd vaccination of either ARCT-154 or placebo at Day 92 followed by placebo at Day 120 in order to compare immunogenicity after 3 injections of ARCT-154 with that after 2 injections. Administration of a 3rd dose of ARCT-154 to participants in Phase 2/3a allows the opportunity to evaluate the neutralizing antibody of activity of a 3rd (booster) dose of ARCT-154 against variants of concern, and in particular the newly identified omicron variant. Early data indicates that neutralizing antibody activity against omicron following two doses of other RNA vaccines may be substantially less than against other variant strains, but that activity following a third dose is considerably improved.

In addition, the principal analysis of Efficacy was changed to be performed as a secondary analysis in the pooled participant populations from Phase 1/2/3a/3b in order to increase statistical power of this analysis. Additionally, enrollment of Phase 3c was terminated at request of Vietnam Ministry of Health after enrollment of ~2,400 of the originally planned 4,000 since 4,000 participants are not needed for assessment of the principal immunogenicity endpoints. Therefore, this amendment updates the number of participants in Phase 3c and clarifies that Phase 3c immunogenicity assessments will be performed in 800 participants in subgroup Phase 3c-1. This amendment also includes administrative changes for consistency of language and changes to the Synopsis for consistency with the changes to the main body outlined below, as well as correction of minor typographical and referencing errors.

Protocol Amendment 7 (Version 8.0, 14 December 2021): Summary of Major Changes

Section Number	Description of Change	Brief Rationale
Cover page	Name of sponsor company updated	Company name change
Section 1.1	Study schematic (Figure 1) updated to reflect new study design	Updated to reflect the current study design in this amendment
Section 2.7	Added rationale for the 3 rd dose for cohorts 2/3a	Updated to reflect the current study design in this amendment

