- **Safety Analysis Set (SAS):** Includes all participants who receive any dose of study vaccine (ARCT-154 or placebo or ChAdOx1). Participants will be analyzed according to the study vaccine received. SAS analysis sets are defined for each Phase of the study as follows:
  - Phase 1/2/3a SAS: this pools data from Phase 1, Phase 2 and Phase 3a participants
  - Phase 3b SAS
  - Phase 3c SAS
  - Pooled SAS: this pools data from Phase 1/2/3a/3b for ARCT-154 and placebo, respectively. It will include evaluations up to Day 92 only (except for unsolicited events)
- **Reactogenicity Analysis Set (RAS):** Includes all participants who receive any dose of study vaccine (ARCT-154 or placebo or ChAdOx1) and provide at least 1 reactogenicity diary report. Participants will be analyzed according to the vaccine received.  
Reactogenicity analysis sets are defined for each Phase of the study as follows:
  - Phase 1/2/3a RAS: this pools data from Phase 1, Phase 2 and Phase 3a participants
  - Phase 2/3a RAS
  - Phase 3b RAS
  - Phase 3c RAS
  - Pooled RAS: this pools data from Phase 1/2/3a/3b for ARCT-154 and placebo, respectively.

For safety analysis sets, SAS and RAS, where participants will be analyzed according to the study vaccine received, in case a participant receives incorrect study vaccine, only data up to the receipt of the incorrect study vaccine (exclusive) will be used in the summaries. If the first dose of vaccine the participant received was the incorrectly assigned one, then only data up to the second dose (exclusive) will be used in the summaries. Outputs for “any dose” that analyze data after any ARCT-154 dose or after any Placebo or ChAdOx1 dose, will include all data after each dose even if participant received an incorrect study vaccine.

Separate listings of safety and immunogenicity data, that are currently planned in this SAP, will be produced for participants receiving at least one incorrect dose of study vaccine. Of note, participants with missing dosing will not be considered as receiving incorrect dosing.

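### Phase 3c exclusion criterion 19 is inverted: as written, it excludes people who have no contraindication to ChAdOx1

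*Protocol*

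**What the plan says.** The exclusion list in Protocol Section 5.1.2 opens with "Individuals meeting any of the following criteria will be excluded from the study". Near its end, under the subheading "Additional Exclusion Criteria for Phase 3c Participants Only", stands a single item, number 19: "No contraindications (as specified in the prescribing information) to receiving the ChAdOx1 vaccine". The synopsis carries the same lead-in, subheading and item.

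Three neighbouring sections determine how that item operates:

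- Section 5.1 allows assignment to treatment only for people who satisfy every inclusion criterion and no exclusion criterion, and adds "Deviations from the inclusion and exclusion criteria are not allowed".
- Section 5.1.1 introduces the inclusion list with "Each participant must meet all the following criteria to be enrolled in this study". None of its six items mentions ChAdOx1.
- Section 5.1.4 defines the consequence: "Screen failures are individuals who fail to meet all inclusion criteria or who meet at least 1 of the exclusion criteria".

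**The concern.** An exclusion criterion should name a condition that disqualifies. Items 1 to 18 all do. Item 19 names a condition that qualifies, so the rule runs backwards.

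The item is an operative eligibility rule for participant safety. Phase 3c randomizes about 2,400 people 1:1, so about 1,200 are assigned to ChAdOx1, and item 19 is the only criterion that refers to that vaccine's label. Once the final SAP drops the Phase 3c immunogenicity and efficacy analyses (Section 7.1), safety and reactogenicity are what the cohort still delivers. Its comparator-specific screen should therefore be right on paper.

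The record is also affected. Against the literal text, a properly enrolled Phase 3c participant met an exclusion criterion, whereas a contraindicated participant enrolled by mistake would show no breach of item 19.

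**Working it through.** The documents give no figure to reproduce. The check is a logical reading followed by a count of what depends on the item.

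**Step 1. Apply the lead-in to item 19.** The rule is: meets the item, therefore excluded.

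| Candidate | Meets item 19 as written? | Result as written | Result intended |
|---|---|---|---|
| No labelled contraindication to ChAdOx1 | Yes | Excluded; screen failure under Section 5.1.4 | Eligible on this item |
| Labelled contraindication to ChAdOx1 | No | Not excluded by this item | Excluded |

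Both rows come out the wrong way round.

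**Step 2. Rule out a text-extraction fault.** The same wording stands in two separate places, Section 5.1.2 and the synopsis, each under the same exclusion lead-in.

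**Step 3. Look for a correction elsewhere.** The inclusion list has no ChAdOx1 item. No other current protocol text restates the rule. SAP Sections 7.1 to 7.3 list many corrections to the protocol, and this is not among them.

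**Step 4. See what other criteria cover.**

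- Criterion 5 concerns reactions to the vaccine or its excipients, but sends the reader to the Investigator's Brochure for components. Protocol Sections 2.8.1 and 6.3 place ChAdOx1 risks and product details in that vaccine's own label.
- Criteria 6 (anaphylaxis to other vaccines), 7 (bleeding disorder) and 9 (investigator judgement) are general.

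Together these give partial cover, and none invokes the ChAdOx1 label.

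**Step 5. Count what depends on the item in the final SAP.**

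- Per-protocol sets (Section 4.1): Phase 3b efficacy, Pooled efficacy, Phase 1 immunogenicity, Phase 2/3a immunogenicity and Phase 1/2/3a immunogenicity. That is 2 + 3 = 5, of which 0 cover Phase 3c.
- Deviations listed as removing a participant from a per-protocol set: 5 for efficacy + 6 for immunogenicity = 11, of which 0 are eligibility violations. The per-protocol definition does require eligible participants, but with no Phase 3c set this has no effect here.
- Phase 3c safety set: "Includes all participants who receive any dose of study vaccine (ARCT-154 or placebo or ChAdOx1"). The reactogenicity set adds one diary report. Neither refers to eligibility.
- Phase 3c immunogenicity and efficacy: not analyzed (Section 7.1).

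The outputs the item can touch are the inclusion/exclusion listing (SAP Section 6.3.1) and the protocol-deviation summary and listing (SAP Sections 4.2 and 6.3.1).

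**The case against.** The strongest reply is that this is an obvious slip with no consequence. The literal rule would have left only contraindicated people eligible for Phase 3c. Yet Protocol Appendix 6 records that "enrollment of Phase 3c was terminated at request of Vietnam Ministry of Health after enrollment of ~2,400 of the originally planned 4,000", so sites evidently used the intended meaning. That closure was already recorded with protocol Version 8.0 of December 2021, and the SAP is dated July 2023, so rewording now protects no one. The ChAdOx1 prescribing information is not among the documents, so it cannot be shown that any labelled contraindication falls outside the general exclusions. Criterion 5 can also fairly be read to include ChAdOx1, because Section 6.2 names it as a study vaccine. Screen-failure reasons, eligibility criteria and deviations will be listed anyway.

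Most of this stands. The size of any safety gap is unknown, nothing in the documents shows that a contraindicated person was enrolled, and no result moves. It is also a drafting error and not a deliberate design decision. These points limit how much the error matters; they do not make the sentence correct. Section 5.1 forbids deviations from the criteria, and a listing of eligibility criteria cannot be interpreted when one criterion states the opposite of what sites applied.

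**Conclusion.** The concern holds: item 19 is wrong as written, in two places, and no current text in the protocol or SAP repairs it. No estimate, confidence interval or power statement changes. The effect is confined to the correctness of a written safety criterion and to the reading of the eligibility and deviation outputs for Phase 3c.

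That sites applied the intended meaning is an inference from completed enrollment; the documents do not state it. Whether the general exclusions already cover every labelled contraindication cannot be judged without the ChAdOx1 label. The error should be corrected because it is certain and nearly free to fix, but it does not threaten the trial's conclusions.

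**What to change.** In Section 5.1.2 and in the synopsis, reword item 19 so that having any contraindication listed in the ChAdOx1 prescribing information is the reason for exclusion. Alternatively, leave the sentence as it is and move it to the inclusion criteria, marked as Phase 3c only.

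Since enrollment is closed, the more useful step is one sentence stating how item 19 was applied at screening, placed with the inclusion/exclusion and protocol-deviation listings (SAP Sections 4.2 and 6.3.1).

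The cost is one line in two places plus that sentence. No analysis, analysis set or program changes.
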